All randomized participants will undergo regular visual assessments of freshly collected urine samples for: 1) the presence or absence of visible blood, and 2) the presence or absence of blood clots. The schedule of assessments for each participant will be determined by the treatment location (inpatient vs outpatient), time on study (through the end of Week 6 [Day 42] vs after Week 6), and status of macroscopic hematuria (unresolved vs resolved), as shown in Table 1. Each time that a participant undergoes a urine visual assessment for Bedi grading, the same sample should be sent for urinalysis.

 Table 1.
 Timing of Visual Urine Assessments with Urinalysis

Treatment	Magragaonia	Time on Study		
Location	Macroscopic Hematuria [1]	Through the End of Week 6 (Day 42)	After Week 6 (Day 43)	
Unresolved Inpatient		Bedi assessment with U/A 3 × per week	Bedi assessment with U/A 2 × per week ≥2 days apart	
	Resolved	Bedi assessment with U/A 1 × per week	Bedi assessment with U/A 1 × per week	
Outpatient	Unresolved	Hemostick daily; Bedi assessment with U/A 1 × per week	Hemostick 2 × per week ≥2 days apart; Bedi assessment with U/A 1× per week	
Outpatient	Resolved	Hemostick 1× per week; Bedi assessment with U/A 1 × per week	Hemostick 1 × per week; Bedi assessment with U/A at Week 12 and 24 study visits	

^[1] Resolved macroscopic hematuria is defined as resolution to Grade 0 or 1 on the Bedi scale as assessed by an HCP on the study team on 2 consecutive visual urine assessments \geq 2 days apart without continuous bladder irrigation or nephrostomy tubes. However, if a participant has nephrostomy tubes that are capped, Bedi assessments may be performed, including for the purpose of assessing for resolution.

Abbreviations: HCP = healthcare provider; U/A = urinalysis

In support of the key secondary objective, bladder pain will be assessed using age-appropriate COAs.

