2.2 Study Design

2.2.1 Overview

This is a Phase 3, multicenter, double-blind, placebo-controlled trial to assess the efficacy and safety of PSL compared to placebo for the treatment of participants with virus-associated HC following allogeneic hematopoietic cell transplant (HCT).

The study hypothesis is that the administration of PSL to participants with virus-associated HC will demonstrate superiority for the time to resolution of HC (as measured by resolution of macroscopic hematuria) compared to participants treated with placebo. The primary hypothesis will be tested in participants with BKV viruria to demonstrate superiority over placebo in this population (BK Intent-to-Treat [ITT] Population). The analysis will also be conducted in all participants with any virus-associated HC (BKV, AdV, CMV, HHV-6, JCV, and/or EBV) in order to evaluate efficacy in this broader population (overall ITT Population).

Participants who meet all of the inclusion criteria and none of the exclusion criteria will be randomized in a sequence in the sequential infusions of PSL cells or placebo and will be monitored for resolution of macroscopic hematuria as defined by the primary endpoint. Randomization will be stratified by

In the dosing strategy being evaluated in this study, all participants will receive infusions of either PSL or placebo separated by (± 3) days.

The specific PSL cell line for infusion will be selected using an electronic-based software system (CytoMatch)

. Cryopreservation media

(without cells) will serve as the placebo and will be identical in volume and appearance to PSL.

AlloVir, Inc.	Statistical Analysis Plan
AVM-003-HC	V1.0 14 November 2023

All randomized participants will undergo regular visual inspections of freshly collected urine samples for: 1) the presence or absence of visible blood, and 2) the presence or absence of blood clots. The schedule of assessments will be determined by the treatment location (inpatient vs. outpatient), time on study (through the end of Week 6 [Day 42] vs. after Week 6), and status of macroscopic hematuria (unresolved vs. resolved), as shown in Table 1. Each time that a participant undergoes a urine visual assessment for Bedi grading, the same sample should be sent for urinalysis.

Treatment	Maaraaania	Time on Study		
Location	Hematuria [1]	Through the End of Week 6 (Day 42)	After Week 6	
Inpatient	Unresolved	Bedi assessment with U/A 3 × per week	Bedi assessment with U/A 2 × per week ≥2 days apart	

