2.3.2 Secondary Efficacy Endpoints

The key secondary endpoint is the time to resolution of bladder pain as measured by ageappropriate COAs. Resolution of pain is defined as participants achieving a score on the relevant COA that does not exceed "mild pain," confirmed with 2 consecutive scores, without use of prescription pain medications (not PRN or "as needed") or the use of supportive bladder care, specifically continuous bladder irrigation and nephrostomy tubes.

Mild bladder pain is defined as:

- In participants ≥12 years of age: a score ≤3 on the worst daily pain question from the Bladder Pain/Interstitial Cystitis Symptom Diary (BPIC SD).
- In participants 3 to 11 years of age: a score ≤2 on the Wong-Baker FACES® Pain Rating Scale.

The analysis will include all participants whose pain scores exceed "mild pain" at randomization, or who are receiving prescription pain medications (not PRN or "as needed") or supportive bladder care at randomization. Use of prescription pain medications (not PRN or "as needed") or supportive bladder care will be considered equivalent to pain that exceeds "mild pain." If the pain scores at randomization are missing, the screening pain scores will be used. Otherwise, the participant will not be included in the analysis.

This endpoint will not be assessed in participants <3 years of age as there is no COA that has been validated for this purpose. Instead, data regarding pain behaviors will be collected in this age group using the Patient-Reported Outcomes Measurement Information System® (PROMIS) Parent Proxy Pain Behavior Short Form.

Additional secondary efficacy endpoints include the following:

- Number of days in the hospital (for any reason including, but not limited to, HC) over the 24-week study period.
- Time to resolution of viremia for each target virus (ie, BKV, AdV, CMV, HHV-6, JCV, and/or EBV) over the 24-week study period (only for participants with detectable viremia at randomization). Evaluation of this endpoint will be based on viremia quantitation performed at the central laboratory. Resolution of viremia will be defined by the lower limits of quantitation (LLOQ) of the assays used (BKV, AdV, CMV, HHV-6, JCV are measured in the plasma, EBV is measured in peripheral blood mononuclear cells).
- Average daily bladder pain over the 24-week study period, without use of prescription pain medications (not PRN or "as needed") or supportive bladder care.

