3.1.5 Strata and Covariates

Randomization will be stratified by

. If there are

discrepancies in stratification factor values between the IRT and the EDC database, the values recorded in the EDC database will be used for all the analyses in this SAP. For deriving cidofovir use within 4 weeks prior to screening or during the screening process, such medication is taken within 4 weeks prior to screening visit through the randomization date.

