3.4.3 Other Efficacy Endpoints

If the result of the key secondary efficacy analyses based on the BK ITT and overall ITT Populations are both statistically significant, a formal hypothesis test will be conducted sequentially of the first other secondary endpoint, number of days in the hospital, based on the BK ITT Population. The analysis will be performed using a linear regression model with terms for treatment and the stratification factors at randomization (defined based on EDC data). This secondary endpoint will be tested at the one-sided 0.025 alpha level. If the result of the analysis based on the BK ITT Population is statistically significant, a formal hypothesis test of this endpoint will be conducted based on the overall ITT Population using a 0.025 alpha level. Supportive analyses will be conducted using the BK mITT, BK PP, and mITT Populations.

The sequential testing described above will control the overall Type I error for these endpoints at the one-sided 0.025 level.

Other continuous and categorical efficacy endpoints (including secondary and exploratory endpoints not selected for hierarchical testing above) will be summarized descriptively by treatment group using appropriate populations. Categorical endpoints will be summarized using the number and percentage of participants within each category.

Time-to-event endpoints will be summarized using Kaplan-Meier estimates. Treatment comparison using a stratified log-rank test adjusted by stratification factors at randomization (defined based on EDC data) at one-sided significance level 0.025 will be reported as well. In addition, the hazard ratio along with the 95% confidence intervals for the true hazard ratio will be calculated using a stratified Cox proportional hazards model with treatment, and other potentially confounding factors.

There is no adjustment for multiplicity in the analyses of these other efficacy endpoints.

Specifically, the following efficacy endpoints will be analyzed based on BK ITT Population unless mentioned otherwise, and equally at the one-sided 0.025 level.

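### Unless inpatient status at randomization is already one of the redacted stratification factors, add it as a prespecified covariate in the hospital-days regression: a modest, nearly free gain in precision.

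*SAP*

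**What the plan says.** SAP 2.3.2 lists the endpoint as "Number of days in the hospital (for any reason including, but not limited to, HC") over 24 weeks. SAP 3.4.3 tests it in the BK ITT Population and then in the overall ITT Population, after hematuria and bladder pain have each succeeded in both populations. On the level it says: "This secondary endpoint will be tested at the one-sided 0.025 alpha level". On the model it says: "The analysis will be performed using a linear regression model with terms for treatment and the stratification factors at randomization". Protocol 9.2.1.3 gives the same model.

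No other covariate is named. On robustness, SAP 3.4.3 says: "Supportive analyses will be conducted using the BK mITT, BK PP, and mITT Populations". These analyses change who is included, not the model. The primary and key secondary endpoints, by contrast, each have a Cox sensitivity analysis for further confounders (SAP 3.4.1 and 3.4.2).

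The stratification factors cannot be read. In SAP 3.1.5 the sentence beginning "Randomization will be stratified by" is blacked out after those words, and the protocol's counterparts are too. One factor can be inferred from a surviving derivation rule: "For deriving cidofovir use within 4 weeks prior to screening or during the screening process".

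Care setting is used elsewhere. SAP 2.2.1 says of the urine checks: "The schedule of assessments will be determined by the treatment location (inpatient vs. outpatient"). SAP 3.4.1 uses it, with the discharge date, to fix the resolution date. It is not among the baseline characteristics named in SAP 3.3.3, a list that is expressly not exhaustive, nor among the subgroups named in 3.4.1.

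**The concern.** The count covers all causes and starts at randomization. A participant in a hospital bed on that day carries the rest of the current stay into the outcome; one at home does not. Care setting is therefore tied to the endpoint before treatment has acted.

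If the model does not hold it fixed, two things follow. The variance that care setting explains stays in the residual, so the standard error of the treatment effect is larger than it need be. And a chance difference between arms in the share of inpatients moves the estimate in that realized trial. With about 105 participants and a noisy count, a free reduction in variance is worth taking. If the baseline table does not show care setting, a reader could not see such an imbalance.

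**Working it through.** **The plan's own figure.** No power, SD or effect size is stated for hospital days. The 86.4% in SAP 2.2.3 belongs to the primary log-rank test. With medians of 12 and 6 weeks and 20% dropout by 24 weeks, expected events are 82.3 at 1:1 and 85.7 at 2:1. Schoenfeld's formula then gives 88.2% and 85.6%, so the figure reproduces within 2 points. It says nothing about hospital days.

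**Inputs.** From the documents: N = 105 in BK ITT and one-sided alpha 0.025. Assumed: inpatient share p, inpatient-outpatient gap d in days, and the SD of hospital days. The allocation ratio is redacted; 1:1 is assumed unless stated.

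**Variance explained, within-group SD 25-30, p = 0.5-0.7, d = 15-25.**
R² = p(1−p)d² / [p(1−p)d² + SD²]
- Lowest (p = 0.7, d = 15, SD = 30): 47.25 / (47.25 + 900) = 0.050
- Highest (p = 0.5, d = 25, SD = 25): 156.25 / (156.25 + 625) = 0.200

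The equivalent gain in sample size is 1/(1−R²): 1/0.950 = 1.05 to 1/0.800 = 1.25.

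**More cautious inputs, total SD 30-40, p = 0.3-0.7, d = 10-20.**
R² = p(1−p)d² / SD²
- Lowest (p = 0.3 or 0.7, d = 10, SD = 40): 21/1600 = 0.013
- Highest (p = 0.5, d = 20, SD = 30): 100/900 = 0.111

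**Effect on power.** Adjustment multiplies the standard error by √(1−R²). For a test that has 80% power without adjustment:

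| R² | SE factor | Power |
|---|---|---|
| 0.02 | 0.990 | 80.8% |
| 0.05 | 0.975 | 82.0% |
| 0.10 | 0.949 | 84.0% |
| 0.20 | 0.894 | 87.9% |

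**Simulation on skewed counts** (60% inpatients, 40% fewer days on PSL, 1:1). Power without and with the covariate:
- 5-day gap: 60.5% and 60.6%
- 10-day gap: 57.3% and 58.9%
- 20-day gap: 53.7% and 57.5%

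With no treatment effect, rejection rates were 2.2-2.5% at 1:1 and 2.4-3.0% at 2:1 (Monte Carlo SE about 0.2 points), similar with and without the covariate.

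**Chance imbalance, 60% inpatients, 1:1.** The SD of the difference in inpatient share is √(0.6 × 0.4 × 4/105) = 0.0956. A difference of 10 percentage points or more is 0.10/0.0956 = 1.05 SDs, with probability about 0.30 (0.32 by exact hypergeometric count). At a 20-day gap, a 10-point difference shifts the unadjusted estimate by 0.10 × 20 = 2 days.

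The unadjusted standard error is total SD × √(4/105) = total SD × 0.195. The first set of inputs gives a total SD of about 26-32.5 days, so 5.1-6.3 days; a total SD of 40 gives 7.8. The range is about 5-8 days, and a 2-day shift is roughly 0.25-0.4 of a standard error.

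**The case against.** **The factor may already be in the model.** A reader might infer that the plan ignores care setting. The documents do not support that. The stratification list is redacted wherever it appears, and if care setting is a stratum the model already adjusts for it. Cidofovir use is visible only because its derivation rule survived redaction, which says nothing about the other factors. Absence from a baseline list that is expressly open-ended is weak evidence. This objection stands, and it makes the point conditional.

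**Imbalance is not bias.** A reader might also infer that an uneven split of inpatients invalidates the test. It does not. Over repeated randomizations the unadjusted estimate is unbiased, and its standard error already allows for chance imbalance. The simulation shows no inflation from leaving the covariate out. This stands too: only precision is at stake.

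**The test is low in the hierarchy.** Hospital days in BK ITT is fifth in the sequence, the trial is not powered on it, and treatment plus strata is a valid model. That limits the importance but does not remove a gain that costs almost nothing.

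**Reach.** A reader might extend the argument to the Cox sensitivity model for the primary endpoint. The reasoning here rests on a current stay counting toward hospital days and gives no ground for changing that model.

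**Conclusion.** The point holds conditionally. The formal hospital-days test adjusts for nothing beyond the stratification factors, and no supportive analysis adds a covariate. If care setting at randomization is not one of those factors, the plan forgoes a predictor that is already recorded and mechanically linked to the outcome.

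The size depends entirely on assumed inputs. The benefit runs from negligible (R² about 0.01) to the equivalent of 25% more participants (R² 0.20). Under the cautious inputs it is roughly 0-4 power points. No primary or key secondary conclusion is affected. This is a worthwhile refinement, not an error that threatens the trial.

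**What to change.** First check the unredacted stratification list. If care setting at randomization is on it, the model needs no change.

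Otherwise:
- In SAP 3.4.3 and Protocol 9.2.1.3, add inpatient/outpatient status at randomization, before the first infusion, as a term in the linear regression for both the BK ITT and the ITT test.
- Add the same variable to the baseline characteristics in SAP 3.3.3, so that any imbalance is visible.

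The cost is one model term and one table row. No new data or participants are needed. The change must be made before unblinding, since adding the term afterwards would look selective.

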The primary efficacy analysis will be conducted after all participants have completed 24 weeks of follow up or have discontinued early from the study. At the primary analysis, the PSL group will be compared to the placebo group in the BK ITT Population using a stratified log-rank test based on the stratification factors at randomization. The study will be considered a success if the one-sided p-value from the stratified log-rank test comparing treatment to control is less than 0.0147 (reduced from 0.025 due to inclusion of an interim analysis based on Pocock method).

If the result of the analysis of the primary efficacy endpoint (ie, time to resolution of macroscopic hematuria) is statistically significant based on the BK ITT Population, a formal hypothesis test will then be conducted of this same endpoint based on the overall ITT Population.

If the result of this analysis is also statistically significant, a formal hypothesis test will be conducted of the key secondary endpoint of time to resolution of bladder pain based on the BK ITT Population in a manner analogous to that for the primary efficacy endpoint. If the result of this analysis is statistically significant, a formal hypothesis test of this same endpoint will be conducted based on the overall ITT Population.

If the results of the analyses of the key secondary efficacy endpoint are statistically significant for both the BK ITT and overall ITT Populations, a formal hypothesis test will be conducted of the first other secondary endpoint, number of days in the hospital, based on the BK ITT Population. The analysis will be performed using a linear regression model with terms for treatment and the stratification factors at randomization. If the result of the analysis based on the BK ITT Population

is statistically significant, a formal hypothesis test of this same endpoint will be conducted based on the overall ITT population.

Other continuous and categorical efficacy endpoints (including secondary and exploratory endpoints not selected for hierarchical testing above) will be summarized descriptively by treatment groups using the mITT Population.

Time-to-event endpoints will be summarized using Kaplan-Meier estimates. In addition, the hazard ratio along with the 95% confidence intervals for the true hazard ratio will be calculated using a Cox proportional hazards model with treatment, stratification factors at randomization, and other potentially confounding factors.

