2.2 Secondary Objectives

The key secondary objective is to compare the time to resolution of bladder pain as measured by Clinical Outcome Assessments (COAs) in recipients of PSL to that in recipients of placebo.

Other secondary objectives include comparisons of the following in recipients of PSL and recipients of placebo:

- To assess number of days in the hospital (for any reason including HC) over the 24-week study period.
- To assess the incidence and severity of acute GVHD and cytokine release syndrome (CRS) over the 24-week study period.
- To assess time to resolution of viremia for all target viruses over the 24-week study period (only for participants with detectable viremia at baseline).
- To assess average daily bladder pain (11-point numeric rating scale [NRS]) over the 6-week period from randomization.

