2.1.2 Secondary Objectives

The key secondary objective is to compare the time to resolution of bladder pain as measured by clinical outcome assessments (COAs) in recipients of PSL to that in recipients of placebo.

Other secondary objectives include comparisons of the following in recipients of PSL and recipients of placebo:

- To assess number of days in the hospital (for any reason including hemorrhagic cystitis [HC]) over the 24-week study period.
- To assess the incidence of acute graft versus host disease (GVHD) and cytokine release syndrome (CRS) over the 24-week study period.
- To assess time to resolution of viremia for each target virus over the 24-week study period (only for participants with detectable viremia at randomization).
- To assess average daily bladder pain over the 24-week study period.
- To assess time to global impression of hemorrhagic cystitis severity of none or mild.

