2.1.3 Exploratory Objectives

The exploratory objectives include comparisons of the following in recipients of PSL and recipients of placebo as measured over the 24-week study period:

- Cumulative days and time to discontinuation of supportive bladder care for HC, specifically continuous bladder irrigation and/or nephrostomy tubes.
- Summary of HC-associated signs and symptoms other than bladder pain.
- Incidence and time to recurrence of HC.
- Incidence and time to recurrence of bladder pain.
- Requiring red blood cell (RBC) and/or platelet transfusions and the number of required RBC and/or platelet transfusions (measured in transfusion units/participant).
- Change in renal function as assessed by estimated glomerular filtration rate (eGFR). For participants requiring dialysis, number of days on dialysis will be captured.

- Time to resolution of BK viruria. Resolution of viruria will be defined by the lower limits of quantitation of the assay used.
- Viremia and viruria with each target virus (ie, BKV, AdV, CMV, HHV-6, JCV, and/or EBV) over time.
- Length of use of any pain medication(s) (IV, oral, or other), including antispasmodics anticholinergics, and beta-3-agonists, used for control of lower abdominal/bladder pain.
- Use of immunosuppressive agents, by specific agent during the study.
- Number of hospitalizations, number of intensive care unit (ICU) stays, and number of days of ICU care for any reason.
- Use of antiviral therapies other than cidofovir with potential activity against at least one target virus by specific agent during the study.
- Overall survival, defined as time to death (from any cause) from the time of randomization in days.
- Incidence of relapse or progression of primary malignancy.
- Overall quality of life as measured by EuroQol 5 Dimensions (EQ-5D) questionnaires.
- Global impression of hemorrhagic cystitis change.

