Time to resolution of viremia for each target virus (ie, BKV, AdV, CMV, HHV-6, JCV, and/or EBV) over the 24-week study period (only for participants with detectable viremia at randomization) will be analyzed using Kaplan-Meier estimates, and treatment effect will be compared using stratified log-rank test and hazard ratio with stratified Cox proportional model. Evaluation of this endpoint will be based on viremia quantitation performed at the central laboratory. Resolution of viremia will be defined by the lower limits of quantitation (LLOQ) of the assays used (BKV, AdV, CMV, HHV-6, JCV are measured in the plasma, EBV is measured in peripheral blood mononuclear cells). Only participants who had viremia at randomization for each target virus will be included in the analysis.

Average daily bladder pain (ie, the participant's average bladder pain over the previous 24 hours) will be recorded daily for the first 6 weeks of the study and once weekly thereafter. The average daily bladder pain will be averaged for each week for the first 6 weeks and starting at Week 7, the single average daily pain score will be recorded. The applicable weekly measures will be summarized by treatment group over the 24-week study period. Only pain assessments

without use of prescription pain medications (not PRN or "as needed") or supportive bladder care will be used.

Time to global impression of hemorrhagic cystitis severity of none or mild, confirmed with 2 consecutive scores, will be analyzed similar to the key secondary endpoint. The analysis will include all the participants who exceed "mild" at randomization. If the scores at randomization are missing, a prior score will be used if available. Otherwise, the participant will not be included in the analysis. Time to resolution will be calculated from the date of randomization to the date of the first time reaching the global impression of hemorrhagic cystitis severity of non or mild, without use of prescription pain medications (not PRN or "as needed") or supportive bladder care. Participants not observed to achieve the threshold will be considered censored at their last follow up.

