Time to resolution of BK viruria will be analyzed using Kaplan-Meier estimates, and treatment effect will be compared using stratified log-rank test and hazard ratio with stratified Cox proportional model. Resolution of viruria is defined by the lower limits of quantitation of the assay used. Resolution of viruria is defined by the lower limits of quantitation of the assay used. Only the participants who had BK viruria at randomization will be included in the analysis. Time to resolution refers to the time from randomization to the initial resolution of viruria.

The numbers and proportions of patients with viremia and viruria with each target virus (ie, BKV, AdV, CMV, HHV-6, JCV, and/or EBV) over time for all the participants as well as for participants who are negative at randomization only.

Length of use of any pain medication(s) (IV, oral, or other), including antispasmodics anticholinergics, and beta-3-agonists, used for control of lower abdominal/bladder pain will be summarized as the total days on any pain medication for each participant.

The use of immunosuppressive agent(s) by specific agent during the study will be summarized by treatment group. The specific dosage information will be listed only.

Number of hospitalizations, number of ICU stays, and number of days of ICU care for any reason will be summarized by treatment group, and reasons will be listed by participant.

Use of antiviral therapies other than cidofovir with potential activity against at least one target virus will be summarized by specific agent during the study. Agents analyzed include foscarnet, ganciclovir, letermovir, maribavir, and valganciclovir. Rd

Overall survival, defined as time to death (from any cause) from the time of randomization in days, will be analyzed as displaying number of participants who died from any cause by week 24 and censored by week 24.

Incidence of relapse or progression of the primary malignancy will also be summarized by treatment group over the 24-week period.

Overall quality of life as measured by appropriate EQ-5D questionnaires will be summarized by treatment for each subdomain over time.

Global impression of change will be summarized by treatment over time.

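### SAP 3.4.3 defaults to the BK ITT Population for non-BK viremia resolution and overall survival, leaving out randomized participants without BKV in urine and departing from the protocol synopsis

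*SAP*

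**What the plan says.** SAP 3.4.3 gives two statements on the analysis set for endpoints outside the testing hierarchy. The general one is open: such endpoints "will be summarized descriptively by treatment group using appropriate populations". The specific one, which introduces the endpoint-by-endpoint list, is not: "the following efficacy endpoints will be analyzed based on BK ITT Population unless mentioned otherwise".

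Two items on that list matter here.

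- **Time to resolution of viremia, by virus.** The paragraph adds one condition, "Only participants who had viremia at randomization for each target virus will be included in the analysis", and names no other population.
- **Overall survival.** It "will be analyzed as displaying number of participants who died from any cause by week 24 and censored by week 24". Again no population is named.

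The SAP objective for the first item (2.1.2) is "To assess time to resolution of viremia for each target virus over the 24-week study period"; Protocol 2.2 has "To assess time to resolution of viremia for all target viruses over the 24-week study period". Both limit the analysis to participants with detectable viremia at the start and neither mentions BK status. Survival is listed among the exploratory objectives in SAP 2.1.3: "Overall survival, defined as time to death (from any cause) from the time of randomization in days".

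The protocol synopsis (Statistical Analyses) says that endpoints outside the hierarchy, including secondary and exploratory ones, "will be summarized descriptively by treatment groups using the mITT Population". Protocol 9.2.1.3 leaves the set open.

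SAP 3.2.2 defines BK ITT by BKV detected in urine on or before randomization. Inclusion criterion 4c (Protocol 4.1) accepts viruria with any one of six target viruses.

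**The concern.** A participant outside BK ITT will ordinarily have entered the trial through AdV, CMV, HHV-6, JCV or EBV. These participants bear directly on the non-BK viremia analyses, yet the default removes them. It also removes them from a survival count that the SAP defines from randomization.

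The endpoints in the hierarchy are treated more broadly. Hematuria resolution, bladder pain and hospital days each have an overall ITT step and an mITT supportive analysis. Resolution of non-BK viremia, where BK status matters least, has no specified all-virus analysis.

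At stake are some precision in small virus-specific analyses, a complete exploratory survival count, and a clear pre-specified population. The documents currently give three answers (mITT, open, BK ITT) and no reason for the narrowest one.

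**Working it through.** **Inputs.** From SAP 2.2.3: about 125 randomized, 105 in BK ITT, 85% of those randomized assumed to fall in BK ITT. The documents give no rate of baseline viremia for any virus, so every rate below is an assumption.

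**1. The plan's own figure.** 105 / 0.85 = 123.5, rounded up to 124, against the stated approximately 125. It reproduces.

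**2. Planned number outside BK ITT.** 125 − 105 = 20; 0.15 × 125 = 18.75; 124 − 105 = 19. So 19 to 20 participants, or 15% to 16% of those randomized.

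**3. Survival.** No further condition applies, so all 19 to 20 are outside the count.

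**4. Viremia resolution.** Only participants viremic with the virus in question at randomization enter, and eligibility requires viruria, not viremia. The number lost over all non-BK viruses is 20 × (share of the non-BK-ITT participants who are viremic):

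| Assumed share viremic | Participants lost (of 20) |
|---|---|
| 10% | 2 |
| 25% | 5 |
| 50% | 10 |
| 75% | 15 |
| 100% | 20 |

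About 20 is therefore a ceiling.

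**5. Precision for one non-BK virus.** Take the standard error as proportional to 1/√(evaluable participants). The ratio of the BK ITT standard error to the all-randomized one is then √(evaluable in all / evaluable in BK ITT).

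- *Equal viremia rate in both groups:* the rate cancels, giving √(125/105) = 1.09. At 30%, for example, 6 of 6 + 31.5 = 37.5 are lost (16%).
- *Non-BK participants spread evenly over five viruses, 4 each, 60% of them viremic, with 20% of BK ITT viremic:* 2.4 of 2.4 + 21 = 23.4 are lost (10%); ratio √(23.4/21) = 1.06.
- *60% of all 20 viremic with the same virus, 20% of BK ITT viremic:* 12 of 12 + 21 = 33 are lost (36%); ratio √(33/21) = 1.25. This needs 12 of 20 participants to share one virus out of five, so it is an extreme case.

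**6. What is not affected.** Both endpoints lie outside the gatekeeping sequence and carry no multiplicity adjustment. The primary test, its alpha and its power do not involve them.

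**The case against.** The best case for the SAP is that Protocol 9.2.1.3 left the population open and the later SAP filled the gap with the primary analysis population. The mITT sentence in the synopsis is phrased for continuous and categorical endpoints, and the time-to-event sentence after it names no set. Non-BK participants are also covered where formal inference is made, through the overall ITT tests.

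Part of this stands. The SAP may choose a population, and nothing confirmatory turns on this one. But the synopsis sentence expressly takes in secondary and exploratory endpoints outside the hierarchy, and mITT is the only set it offers for them. The SAP gives no reason for departing from it, and its own viremia objective has no BK restriction.

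A reader might also infer more than the documents support:

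- *That about 20 participants drop out of a secondary objective.* Only those viremic at randomization could enter that endpoint. The full 19 to 20 are lost only from survival, which is exploratory.
- *That the trial cannot describe activity against the other viruses.* SAP BK ITT is defined by detection of BKV, not by BKV alone or by cause, so participants with BKV plus another virus remain.
- *That deaths of non-BK participants go unreported.* Adverse events leading to death are tabulated, and deaths listed, in the Safety Population (SAP 3.5 and 3.5.1), which covers dosed participants with any virus. What is missing is the count from randomization in everyone randomized.
- *That the viremia and viruria over-time summaries are restricted too.* Their wording in SAP 3.4.3 refers to all participants, which is most naturally an exception to the default.

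**Conclusion.** The point holds as a minor inconsistency in the analysis set. Following SAP 3.4.3 as written, overall survival omits the planned 19 to 20 of about 125 randomized participants without BKV detected in urine. Each non-BK viremia analysis omits those of them viremic with that virus at randomization, at most about 20 in total and possibly only a few.

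The planned count rests on the SAP's 85% assumption. With equal viremia rates inside and outside BK ITT, the loss of precision is about 9% in the standard error; the other assumed cases run from 1.06 to 1.25 times, the last being extreme. Since the actual rates are not in the documents, none of these is an estimate for this trial.

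**What to change.** In SAP 3.4.3, name the overall ITT Population as the analysis set for time to resolution of viremia with AdV, CMV, HHV-6, JCV and EBV and for overall survival. Keep BK ITT as a supportive set for these, and as the main set for BK viremia and BK viruria. State how this relates to the mITT sentence in the protocol synopsis, since ITT and mITT differ by the undosed participants, or give the reason if BK ITT is to be kept. Settle the choice before unblinding so that it cannot depend on the data.

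The cost is one SAP sentence, a line of reconciliation, and running planned tables on a population already defined in SAP 3.2.1. The plan already has viral loads for all six viruses monitored and participants followed for 24 weeks, so no new data are needed.
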